## 6.3.8 ECG

For timing of assessments refer to the study plan (Figure 2).

The 12-lead paper ECGs will be obtained after 10 minutes supine rest at pre-dose and during study days. Only the overall evaluation (normal/abnormal) will be recorded in the CRF.

#### 6.3.9 Vital signs

#### 6.3.9.1 Pulse and blood pressure

For timings of assessments refer to the study plan (Figure 2).

Supine blood pressure and pulse will be measured after at least 10 minutes supine rest on a bed. If possible, the same equipment should be used for each evaluation. It is preferable to avoid the arm with a cannula.

## 6.4 **Pharmacokinetics**

For investigational product administrations, the date and time of the infusion start and stop, as well as start/stop of any infusion interruptions and restart of the infusion, and the actual volume and amount of ceftaroline fosamil infused will be recorded.

#### 6.4.1 Collection of pharmacokinetic samples

Venous blood samples (approximately 4 mL per sample) for the determination of ceftaroline fosamil (the prodrug of ceftaroline), ceftaroline, and ceftaroline M-1 (the metabolite of ceftaroline) concentrations in plasma will be taken at the time points presented in Figure 3.

Urine samples for determination of concentrations of ceftaroline fosamil, ceftaroline, and ceftaroline M-1 in urine will be taken from the total urine sample provided during each collection period presented in Figure 3. Subjects will be required to empty their bladders prior to the start of the urine sample collection and will be asked to drink 240 mL of water after bladder emptying. The weight and the derived volume of the urine collected over each urine collection interval will be calculated.

The date and time of collection of each blood sample will be recorded. The start and stop date and time of collection of each pooled urine sample will also be recorded.

Samples will be collected, labelled, stored, and shipped as detailed in the Laboratory Manual.

For blood volume see Section 7.1.

#### 6.4.2 Determination of drug concentration in pharmacokinetic samples

Samples for determination of ceftaroline fosamil, ceftaroline, and ceftaroline M-1 concentration in plasma and urine will be analysed by on behalf of AstraZeneca, using an appropriate bioanalytical method. Full details of the analytical method used will be described in a separate bioanalytical report.

All samples still within the known stability of the analytes of interest (ie, ceftaroline fosamil, ceftaroline, and ceftaroline M-1) at time of receipt by the bioanalytical laboratory will be analysed.

For each placebo subject, samples will only be analysed on a 'for cause' basis, eg, if no quantifiable concentrations were observed in a subject's samples when the drug was expected to be present.

Additional analyses may be conducted on the biological samples to further investigate the presence and/or identity of drug metabolites. Any results from such analyses may be reported separately from the clinical study report.

Additional analyses will be conducted on the biological samples to investigate the reproducibility of the analytical results in incurred samples. Any results from such analyses will only be used to confirm the reproducibility of the method and will be reported in a separate table in the bioanalytical study contribution report.

#### 6.5 Biomarkers

#### 6.5.1 Collection of exploratory biomarker sample

A total of 40 mL blood will be collected at each of the time points presented in the study plan (Figure 2) for potential future exploratory research aimed at exploring biomarkers involved in the PK, PD, safety, tolerability, and efficacy of ceftaroline fosamil.

Samples will be collected, labelled, stored, and shipped as detailed in Laboratory Manual.

For blood volume see Table 4.

## 7. BIOLOGICAL SAMPLING PROCEDURES

## 7.1 Volume of blood

The total volume of blood that will be drawn from each subject is presented in Table 4.

Assessment		Sample volume (mL) a	No. of samples	Total volume (mL)
Safety	Clinical chemistry	2.5	5	12.5
	Haematology	2	5	10
	Serology	2.5	1	2.5
Follicle-stimulating hormone and serum pregnancy test b		2.5	1	2.5
Pharmacokinetic	28			
Cohort 1 (600 mg 1-hour infusion q12h)		4	44	176
Cohort 2 (600 mg 2-hour infusion q8h)		4	43	172
Exploratory biomarker		40	2	80
Total				283.5 / 279.5

Table 4Volume of blood to be drawn from each subject

a If a cannula is used, an additional 1 mL of blood will be collected to flush the cannula at each sample time point.

b Female subjects only.

The number of samples taken, as well as the volume required for each analysis, may be changed during the study. However, the maximum volume to be drawn from each subject will not exceed 450 mL, ie, the same volume as would be drawn during a regular blood donation.

## 7.2 Handling, storage and destruction of biological samples

The samples will be used up or disposed of after analyses or retained for further use as described in this section.

#### 7.2.1 Safety samples

Safety samples will be disposed of after analysis.

#### 7.2.2 Pharmacokinetic samples

Samples will be disposed of after the CSR has been finalised, unless retained for future analyses.

Incurred sample reproducibility analysis, if any, will be performed alongside the bioanalysis of the test samples and reported in a separate Bioanalytical Report.

Additional analysis may be conducted on the biological samples to further investigate the identity of drug metabolites. The biological samples may be retained for a maximum of 2 years following the finalisation of the clinical study report. Any results from such analyses will be reported separately from the clinical study report

## 7.2.3 Exploratory biomarker samples

Biological samples for biomarker research can be retained on behalf of AstraZeneca for a maximum of 15 years following the last subject's last visit in the study. The results from future analysis will not be reported in the CSR, but separately in a Scientific Report.

## 7.3 Labelling and shipment of biohazard samples

The Investigator ensures that samples are labelled and shipped in accordance with the Laboratory Manual and the Biological Substance, Category B Regulations (materials containing or suspected to contain infectious substances that do not meet Category A criteria), see Appendix C International Air Transport Association (IATA) 6.2 Guidance Document.

Any samples identified as Infectious Category A materials are not shipped and no further samples will be taken from the subject unless agreed with AstraZeneca and appropriate labelling, shipment, and containment provisions are approved.

# 7.4 Chain of custody of biological samples

A full chain of custody is maintained for all samples throughout their life cycle.

The Investigator keeps full traceability of collected biological samples from the subjects while in storage at the study centre until shipment or disposal (where appropriate) and keeps documentation of receipt of arrival.

The sample receiver keeps full traceability of the samples while in storage and during use until used or disposed of or until further shipment and keeps documentation of receipt of arrival.

AstraZeneca oversees the entire life cycle through internal procedures, monitoring of the study centre, and auditing of external laboratory providers.

Samples retained for further use are registered in the AstraZeneca biobank system during the entire life cycle of the sample.

## 7.5 Withdrawal of informed consent for donated biological samples

If a subject withdraws consent to the use of donated biological samples, the samples will be disposed of/destroyed, if not already analysed and the action documented. If samples are already analysed, AstraZeneca is not obliged to destroy the results of this research.

As collection of the safety laboratory and PK samples is an integral part of the study, the subject is then withdrawn from further study participation.

The Investigator will:

- Ensure that the subject's withdrawal of informed consent for the use of donated samples is notified immediately to AstraZeneca
- Ensure that biological samples from that subject, if stored at the study centre, are immediately identified, disposed of or destroyed, and the action documented
- Ensure that the laboratory(ies) holding the samples is/are informed about the withdrawn consent immediately and that samples are disposed of or destroyed, the action documented, and the signed document returned to the study centre
- Ensure that the subject and AstraZeneca are informed about the sample disposal

AstraZeneca ensures the laboratory(ies) holding the samples is/are informed about the withdrawn consent immediately and that samples are disposed of or destroyed and the action documented and returned to the study centre.

# 8. ETHICAL AND REGULATORY REQUIREMENTS

## 8.1 Ethical conduct of the study

The study will be performed in accordance with ethical principles that have their origin in the Declaration of Helsinki and are consistent with ICH/ GCP, applicable regulatory requirements and the AstraZeneca policy on Bioethics and Human Biological Samples.

## 8.2 Subject data protection

The Informed Consent Form will incorporate (or, in some cases, be accompanied by a separate document incorporating) wording that complies with relevant data protection and privacy legislation.

## 8.3 Ethics and regulatory review

An Ethics Committee (EC) should approve the final CSP, including the final version of the Informed Consent Form and any other written information and/or materials to be provided to the subjects. The Investigator will ensure the distribution of these documents to the applicable EC and to the study centre staff.

The opinion of the EC should be provided in writing. The Investigator should submit the written approval to AstraZeneca before enrolment of any subject into the study.

The EC should approve all advertising used to recruit subjects for the study.

AstraZeneca should approve any modifications to the Informed Consent Form needed to meet local requirements.

If required by local regulations, the CSP should be re-approved by the EC annually.

Before enrolment of any subject into the study, the final CSP, including the final version of the Informed Consent Form, is approved by the national regulatory authority or a notification to the national regulatory authority is done, according to local regulations.

AstraZeneca will handle the distribution of any of these documents to the national regulatory authorities.

AstraZeneca will provide regulatory authorities, the EC, and the Investigator with safety updates/reports according to local requirements, including suspected unexpected serious adverse reactions, where relevant.

## 8.4 Informed consent

Any incentives for subjects who participate in the study as well as any provisions for subjects harmed as a consequence of study participation should be described in the informed consent form that is approved by an EC.

The Investigator will:

- Ensure that each subject is given full and adequate oral and written information about the nature, purpose, possible risk, and benefit of the study
- Ensure that each subject is notified that they are free to withdraw from the study at any time
- Ensure that each subject is given the opportunity to ask questions and allowed time to consider the information provided
- Ensure each subject provides signed and dated informed consent before conducting any procedure specifically for the study
- Ensure the original, signed Informed Consent Form(s) is/are stored in the Investigator's Study File
- Ensure a copy of the signed Informed Consent Form(s) is/are given to the subject.

## 8.5 Changes to the protocol and Informed Consent Form

Study procedures will not be changed without the mutual agreement of the Investigator and AstraZeneca.

If there are any substantial changes to the CSP, then these changes will be documented in a CSP Amendment, and where required in a new version of the CSP (Revised Protocol).

The Amendment should be approved by the EC and if applicable, also the national regulatory authority, before implementation. Local requirements should be followed for Revised Protocols.

AstraZeneca will distribute any subsequent Amendments and new versions of the CSP to the Investigator. For distribution to the EC see Section 8.3.

If a CSP Amendment requires a change to the Informed Consent Form, AstraZeneca and the EC should approve the revised Informed Consent Form before the revised form is used.

If local regulations require, any administrative change will be communicated to or approved by the EC.

# 8.6 Audits and inspections

Authorised representatives of AstraZeneca, a regulatory authority, or an EC may perform audits or inspections at the study centre, including source data verification. The purpose of an audit or inspection is to systematically and independently examine all study-related activities and documents, to determine whether these activities were conducted, and data were recorded, analysed, and accurately reported according to the CSP, GCP, guidelines of the ICH, and any applicable regulatory requirements. The Investigator will contact AstraZeneca immediately if contacted by a regulatory agency about an inspection at the study centre.

# 9. STUDY MANAGEMENT

will manage the study on behalf of AstraZeneca.

## 9.1 **Pre-study activities**

Before the first subject is entered into the study, it is necessary for a representative of AstraZeneca to visit the stud centre to:

- Determine the adequacy of the facilities
- Determine availability of subjects appropriate for the study
- Discuss with the Investigator (and other staff involved with the study) their responsibilities with regard to CSP adherence, and the responsibilities of AstraZeneca or its representatives. This will be documented in a Clinical Study Agreement between AstraZeneca and the Investigator

# 9.2 Training of study site staff

Before the first subject is entered into the study, an AstraZeneca representative will review and discuss the requirements of the CSP and related documents with the study staff and also train them in any study-specific procedures and system(s) utilised.

The Investigator will ensure that appropriate training relevant to the study is given to all of these staff, and that any new information relevant to the performance of this study is forwarded to the staff involved.

The Investigator will maintain a record of all individuals involved in the study (medical, nursing, and other staff).

## 9.3 Monitoring of the study

During the study, an AstraZeneca representative will have regular contacts with the study centre, including visits to:

- Provide information and support to the Investigator
- Confirm that facilities remain acceptable
- Confirm that the study staff is adhering to the CSP, that data are being accurately and timely recorded in the CRFs, that biological samples are handled in accordance with the Laboratory Manual and that investigational product accountability checks are being performed
- Perform source data verification (a comparison of the data in the CRFs with the subject's medical records at the hospital or practice, and other records relevant to the study) including verification of informed consent of participating subjects. This will require direct access to all original records for each subject (eg, clinic charts)
- Ensure withdrawal of informed consent to the use of the subject's biological samples is reported and biological samples are identified and disposed of/destroyed accordingly, and the action is documented, and reported to the subject.

The AstraZeneca representative will be available between visits if the Investigator or other staff at the study centre needs information and advice about the study conduct.

#### 9.3.1 Source data

Refer to Clinical Study Agreement for location of source data.

#### 9.4 Study agreements

The Principal Investigator should comply with all the terms, conditions, and obligations of the Clinical Study Agreement or equivalent for this study. In the event of any inconsistency between this CSP and the Clinical Study Agreement, the CSP shall prevail with respect to the

conduct of the study and the treatment of subjects and in all other respects, the terms of the Clinical study Agreement shall prevail.

Agreements between AstraZeneca and the Principal Investigator should be in place before any study-related procedures can take place, or subjects are enrolled.

#### 9.4.1 Archiving of study documents

The Investigator follows the principles outlined in the Clinical Study Agreement.

## 9.5 Study timetable and end of study

The end of the study is defined as "the last visit of the last subject undergoing the study".

The study is expected to start in Q2 2012 and to end by Q4 2012.

The study may be terminated if the study procedures are not being performed according to GCP, or if recruitment is slow. AstraZeneca may also terminate the entire study prematurely if concerns for safety arise within this study or in any other study with ceftaroline fosamil.

# **10. DATA MANAGEMENT**

Data management will be performed by.

When the completed paper CRFs have been scanned and indexed, the data are entered into the study database and proofread.

The data collected through third party sources will be obtained and reconciled against study data.

Adverse events and medical/surgical history will be classified according to the terminology of the latest version the Medical Dictionary for Regulatory Activities (MedDRA). Medications will be classified according to the AstraZeneca Drug Dictionary. All coding will be performed by Quintiles.

Data queries will be raised for inconsistent, impossible or missing data. All entries to the study database will be available in an audit trail.

The data will be validated as defined in the Data Management Plan. Quality control procedures will be applied to each stage of data handling to ensure that all data are reliable and have been processed correctly.

When all data have been coded, validated, signed and locked, clean file will be declared.

Evaluation and calculation of variables

# **10.1** Calculation or derivation of safety variable(s)

## 10.1.1 Other significant adverse events

During the evaluation of the AE data, an AstraZeneca medically qualified expert will review the list of AEs that were not reported as SAEs and AEs leading to premature discontinuation. Based on the expert's judgement, significant AEs of particular clinical importance may, after consultation with the CPA Physician, be considered OAEs and reported as such in the CSR. A similar review of laboratory, vital signs, and ECG data will be performed for identification of OAEs.

Examples of these are marked haematological and other laboratory abnormalities, and certain events that lead to intervention (other than those already classified as serious), dose reduction, or significant additional treatment.

# **10.2** Calculation or derivation of pharmacokinetic variables

Pharmacokinetic analysis of the plasma and urine concentration data for ceftaroline fosamil (the prodrug of ceftaroline), ceftaroline, and ceftaroline M-1 (the metabolite of ceftaroline) will be performed at Standard Operating Procedures and Work Instructions will be used as the default methodology if not otherwise specified. The actual sampling times (in unit of hour) will be used in the plasma PK parameter calculations. In addition, for the purpose of calculating time deviations and graphical presentations of the concentration versus time profiles, the nominal time will be converted to unit of hour for PK protocol time points that are in unit of minute.

Pharmacokinetic parameters will be derived using non-compartmental methods with WinNonlin® Professional Version 5.2, or higher, (Pharsight Corp., Mountain View, California, USA). All PK computations will be performed using WinNonlin® Professional Version 5.2, or higher; or SAS® Version 9.2, or higher (SAS Institute Inc., Cary, North Carolina, USA). Graphics may be prepared with SAS® Version 9.2, or higher; or SigmaPlot® 9.0, or higher (Systat Software Inc., San Jose, California, USA).

For missing samples or samples collected close to but not exactly at the end of the infusion, ceftaroline fosamil concentrations at the end of infusion will not be imputed unless warranted by the data. If a concentration of ceftaroline fosamil at the end-of-infusion needs to be estimated, the imputation will be in accordance with procedures described in Quintiles Standard Operating Procedures. The decision to impute a missing end-of-infusion value will be made on a case-by-case basis and documented in the study report. In brief, the estimation steps are as follows:

- 1. Analyse the concentration-time data using an intravenous (IV) bolus model by setting the end-of-infusion time as the dosing time
- 2. Back-extrapolate the concentration at the time of dosing (ie, the end-of-infusion concentration)

- 3. Augment the original concentration-time data set by inserting the back-extrapolated end-of-infusion concentration
- 4. Process the augmented data set with an IV infusion model

Any imputed values for ceftaroline fosamil will solely be used for PK parameter calculations and will not be included in any summary or inferential statistics. Imputed values will be listed separately in the study report. Imputations for the end-of-infusion concentrations will not be performed for ceftaroline and ceftaroline M-1.

Where possible, the following plasma and urine PK parameters will be determined for ceftaroline fosamil (the prodrug of ceftaroline), ceftaroline, and ceftaroline M-1, unless otherwise noted. Other PK parameters may also be calculated if deemed appropriate. The molecular weights to be applied in the PK calculations are 684.7 for ceftaroline fosamil, 604.7 for ceftaroline and 622.7 for ceftaroline M-1.

#### Following the single-dose part in both cohorts of the study:

The following plasma PK parameters of all 3 analytes on Day 1 will be calculated:

- Maximum plasma concentration ( $C_{max}$ ,  $\mu g/mL$ )
- Time to maximum concentration  $(t_{max}, h)$
- Area under the plasma concentration-time curve from zero to infinity (AUC,  $\mu g \cdot h/mL$ ).
- Area under the plasma concentration-time curve from zero to time of the last quantifiable concentration  $[AUC_{(0-t)}, \mu g \cdot h/mL]$
- Area under the plasma concentration-time curve from zero to 12 hours after the start of the infusion  $[AUC_{(0-12)}, \mu g \cdot h/mL]$  (to be calculated for Cohort 1 only)
- Area under the plasma concentration-time curve from zero to 8 hours after the start of the infusion  $[AUC_{(0-8)}, \mu g \cdot h/mL]$  (to be calculated for Cohort 2 only)
- Apparent terminal rate constant ( $\lambda_z$ , 1/h)
- Terminal half-life ( $t_{1/2\lambda z}$ , h), determined as  $\ln(2)/\lambda_z$
- Metabolite/parent Cmax ratios of ceftaroline/ceftaroline fosamil and ceftaroline M-1/ceftaroline (RM/D,Cmax) (adjusted for differences in molecular weights)
- Metabolite/parent AUC ratios of ceftaroline/ceftaroline fosamil and ceftaroline M-1/ceftaroline (RM/D,AUC) (adjusted for differences in molecular weights)

In addition, the following plasma PK parameters will be calculated for ceftaroline and ceftaroline fosamil:

- Mean residence time (MRT, h)
- Total body clearance of drug from plasma (CL for ceftaroline fosamil, apparent CL for ceftaroline [L/h])
- Volume of distribution based on the terminal phase ( $V_z$  for ceftaroline fosamil, apparent  $V_z$  for ceftaroline [L])
- Volume of distribution at steady state (Vss for ceftaroline fosamil, apparent Vss for ceftaroline [L[)

The following urine PK parameters on Day 1 will be calculated for all 3 analytes:

- Amount of analyte excreted in the urine (Ae, mg). The amount will be calculated for each interval and cumulatively
- Fraction of dose excreted into urine  $(f_e,\%)$  calculated as  $A_e$  divided by dose, for each interval and cumulatively
- Total fraction of dose excreted in urine  $(f_{e,total},\%)$  calculated as (ceftaroline fosamil  $f_e$ +ceftaroline  $f_e$ +M-1  $f_e$ ), for each interval and cumulatively
- Renal clearance (CLR, L/h), calculated as cumulative Ae over 24 hoursdivided by AUC(0-t) over 24 hours

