- Volume of distribution at steady state (Vss for ceftaroline fosamil, apparent Vss for ceftaroline [L])

The following urine PK parameters will be calculated for Day 8:

- Amount of analyte excreted in the urine (Ae,ss, mg); the amount will be calculated for each interval and cumulatively up to the end of the dosing interval (12 hours for Cohort 1 and 8 hours for Cohort 2)
- Fraction of dose excreted into urine  $(f_{e,ss},\%)$  calculated as  $A_{e,ss}$  divided by dose for each interval and cumulatively up to the end of the dosing interval (12 hours for Cohort 1 and 8 hours for Cohort 2)
- Total fraction of dose excreted in urine  $(f_{e,ss,total},\%)$  calculated as (ceftaroline fosamil  $f_{e,ss}$ +ceftaroline  $f_{e,ss}$ +M-1  $f_{e,ss}$ ) for each interval and cumulatively
- Renal clearance (CLR,ss, L/h), calculated as cumulative Ae,ss divided by AUCτ over 12 hours for Cohort 1; and cumulative Ae,ss divided by AUCτ over 8 hours for Cohort 2

The following PK parameters from both the single- and multiple-dose parts of the study will be calculated for diagnostic purposes and listed but not summarised:

- The time interval ( $\lambda_z$  upper and lower) of the log-linear regression to determine  $\lambda_z$
- Number of data points ( $\lambda_z$ , N) included in the log-linear regression analysis to determine  $\lambda_z$ . A minimum of 3 data points will be used.
- Goodness of fit statistic for calculation of  $\lambda_z$  (Rsq). If Rsq is 0.80 or less,  $\lambda_z$  and related parameters will not be reported.
- The percent of AUC which is extrapolated to infinity (AUCex, %). If the extrapolated area ( $C_{last}/\lambda_z$ ) is greater than 20% of AUC, then AUC and related parameters will be not reported.

The linear up/log down trapezoidal summation method will be used for calculation of all areas under the curve.

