#### 12.2 Overdose

- An overdose with associated AEs is recorded as the AE diagnosis/symptoms on the relevant AE modules in the CRF and on the Overdose CRF module
- An overdose without associated symptoms is only reported on the Overdose CRF module

If an overdose on an AstraZeneca investigational product occurs during the course of the study, then the Investigator or other study centre staff will inform the appropriate AstraZeneca representatives within 1 day, ie, immediately but no later than the end of the next business day of when he/she becomes aware of it.

The designated AstraZeneca representative works with the Investigator to ensure that all relevant information is provided to the AstraZeneca Patient Safety data entry site.

No specific information is available on the treatment of an overdose with ceftaroline. There were no reports of an acute overdose of ceftaroline in clinical studies. In the event of an acute overdose, ceftaroline should be discontinued and general supportive treatment given. Ceftaroline can be removed by haemodialysis. In subjects with end stage renal disease administered 400 mg of ceftaroline fosamil, the mean total recovery of ceftaroline in the dialysate following a 4-hour haemodialysis session started 4 hours after dosing was 76.5 mg (21.6% of the dose). However, no information is available on the use of haemodialysis to treat an overdose.

For overdoses associated with SAE, standard reporting timelines apply, see Section 6.3.5. For other overdoses, reporting should be done within 30 days.

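### The formula for the fraction of dose excreted in urine has no molecular-weight term; taken literally, it understates ceftaroline by 11.7% and M-1 by 9.1%

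*Protocol*

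**What the plan says.** All of this is in the protocol.

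- **Section 10.2, single-dose urine parameters.** Ae is given in mg for each of the three analytes: "The amount will be calculated for each interval and cumulatively". The fraction fe is Ae "divided by dose, for each interval and cumulatively". The parameter called "Total fraction of dose excreted in urine" (fe,total) is the plain sum of the three fe values.
- **Section 10.2, Day 8 urine parameters.** fe,ss is Ae,ss "divided by dose for each interval and cumulatively up to the end of the dosing interval", and fe,ss,total is again a plain sum.
- **Section 10.2, metabolite/parent ratios.** The Cmax and AUC ratio bullets, in both the single-dose and the multiple-dose lists, say "adjusted for differences in molecular weights". None of the fe, fe,ss or total bullets does.
- **Section 10.2, introductory paragraph.** It opens with a scope that includes urine ("the following plasma and urine PK parameters will be determined for ceftaroline fosamil" and the other two analytes) and ends: "The molecular weights to be applied in the PK calculations are 684.7 for ceftaroline fosamil, 604.7 for ceftaroline and 622.7 for ceftaroline M-1".
- **Section 12.2 (Overdose).** After 400 mg of ceftaroline fosamil, mean recovery of ceftaroline in dialysate "was 76.5 mg (21.6% of the dose").
- **Sections 3.1 and 5.5.2.** Each infusion is 600 mg of ceftaroline fosamil, which is the prodrug.

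**The concern.** The numerator of fe is a mass of ceftaroline, M-1 or prodrug. The only dose that the protocol names is a mass of prodrug. The three molecules differ in weight, so a mass ratio is not the fraction of the administered dose recovered as that analyte, and adding three such ratios mixes different units of substance. The explicit adjustment on the neighbouring ratio bullets makes its absence from the urine bullets look deliberate, and a programmer could reasonably follow the formula as printed.

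Urinary recovery is a named PK outcome on Days 1 and 8 under the secondary objective, for a drug that Section 1.1 describes as eliminated mainly by the kidney. On the literal formula, complete recovery as ceftaroline would be reported as 88% of the dose, which a reader could take as evidence of another elimination route. The results would also be on a different basis from the recovery figure in Section 12.2.

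**Working it through.** **Inputs**

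- Molecular weights (Section 10.2): prodrug 684.7, ceftaroline 604.7, M-1 622.7.
- Dose (Section 3.1): 600 mg prodrug.
- Reference recovery (Section 12.2): 76.5 mg ceftaroline after 400 mg prodrug, stated as 21.6%.

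**Formulas**

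- Literal reading: fe = 100 x Ae / dose, both in mg.
- Molar: fe = 100 x (Ae / MW of analyte) / (dose / 684.7).
- Literal divided by molar = MW of analyte / 684.7.

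**Step 1: reproduce the protocol's own recovery figure**

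- Literal: 76.5 / 400 = 19.1%. This does not match 21.6%.
- Molar: 400 x 604.7/684.7 = 353.26 mg ceftaroline equivalents, and 76.5 / 353.26 = 21.66%. Allowing for the rounding of 76.5 (76.45 to 76.55), the range is 21.64% to 21.67%. This matches 21.6% to within 0.1 point.

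**Step 2: size per analyte under the literal reading**

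| Analyte | MW / 684.7 | Understatement of fe | 600 mg prodrug equals |
|---|---|---|---|
| Prodrug | 1.0000 | none | 600 mg |
| Ceftaroline | 604.7/684.7 = 0.8832 | 11.7% | 529.9 mg |
| M-1 | 622.7/684.7 = 0.9094 | 9.1% | 545.7 mg |

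The understatements are relative, not percentage points of dose.

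**Step 3: size for the total**

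With no prodrug in urine, the total is low by between 9.1% (all M-1) and 11.7% (all ceftaroline). Section 1.1 gives less than 1% prodrug in monkey urine and none in rat urine. The protocol gives no human urinary recoveries, so the following are assumptions:

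- 65% ceftaroline + 15% M-1 = 80% molar. Literal: 0.65 x 0.8832 + 0.15 x 0.9094 = 71.0%, which is 11.2% low.
- 50% ceftaroline + 10% M-1 = 60% molar. Literal: 53.25%, which is 11.25% low.
- 5% prodrug + 60% ceftaroline + 5% M-1 = 70% molar. Literal: 62.5%, which is 10.7% low.

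**Step 4: what is not affected**

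- Ae is an amount in mg and needs no conversion.
- Renal clearance is Ae over AUC of the same analyte, so the molecular weight cancels.
- The factor for each analyte is a constant, so ratios of that analyte's fe between Day 1 and Day 8, or between Cohort 1 and Cohort 2, are unchanged. The factor for the total can move slightly with the mix of analytes, between 0.883 and 0.909 when there is no prodrug.

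**The case against.** The best reply is that the protocol already supplies the correction. The molecular weights are said to apply to the PK calculations, in a paragraph that covers urine as well as plasma and does not confine them to the ratios. The fe bullets say only dose, without stating that it means prodrug mass. Section 12.2 uses equally plain wording for a figure on the molar basis, which suggests that the sponsor's convention is molar. Standard procedures are the default method, and a statistical analysis plan may spell this out.

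Part of this stands. A reader might infer that the protocol forbids the conversion and that recovery will certainly be understated. The documents do not support that: the correction is compatible with the text, and the bias arises only if the formula is taken at face value.

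The rest does not remove the point. The sentence with the weights does not say which parameters use them, while the bullets that follow flag the adjustment for the ratios only. Standard procedures apply only where the protocol does not specify otherwise, and for fe it gives a formula. The Section 12.2 figure shows that the printed formula and the convention used elsewhere in the same document give different answers. The complaint is about a formula that is stated, not about a detail left to a later plan.

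A reader might also extend the point to apparent CL, Vz and Vss of ceftaroline. The protocol gives no formula for these, so it states nothing wrong there.

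**Conclusion.** The point holds as a defect of definition. The printed fe and fe,ss formulas omit a molecular-weight term that the neighbouring ratio bullets state and that the recovery figure in Section 12.2 implies.

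The two readings differ by fixed factors: 0.883 for ceftaroline and 0.909 for M-1. The total differs by about 9-12% if prodrug in urine is negligible, and by less if it is not. The factors use only the protocol's molecular weights. The range for the total rests on the assumption about prodrug, for which the protocol has animal data only.

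Severity is moderate to minor. Urinary recovery is one of many descriptive secondary PK outcomes. No hypothesis test, sample size or safety rule depends on it, and anyone with the stated molecular weights could convert each analyte's result afterwards.

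**What to change.** In Section 10.2, in the Day 1 and Day 8 urine lists, replace the definition with: fe (and fe,ss) = 100 x (Ae / MW of analyte) / (dose of ceftaroline fosamil / 684.7), for each interval and cumulatively. Define fe,total and fe,ss,total as the sum of these molar fractions over the three analytes. Equivalently, multiply Ae by 684.7/604.7 for ceftaroline and by 684.7/622.7 for M-1 before dividing by the prodrug dose. Leave Ae in mg and renal clearance as they are.

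The cost is a wording change in the protocol, carried into any analysis plan and the PK programming. It needs no new samples, assays or subjects.
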